13.1.5 Assessment of risk and burden

13.1.5.1 Risk assessment

Qualitatively and quantitatively the composition of the test product **sector** is the same as that of Silcap lice shampoo which is already licensed in at least 40 countries for the treatment of head lice in children of 1 year and older.

GOLDGEIST[®] FORTE is already licensed for the treatment of head lice, pubic lice and clothes lice.

Furthermore, the treatments follows the recommendations on the instruction for use and will be applied by trained study staff, thus a decreased general risk in comparison to a home-based usage will be expected.

Due to the short treatment duration, the low concentrations of the active substances, its limited local administration and the minimal absorption of the drug even in irritated skin, there is only a low risk of systemic availability due to penetration. Thus systemic side effects are not expected, neither for adults nor infants.

Nevertheless all patients will be observed for signs of clinical toxicity during the entire study. Among others, checks for general well-being will be performed at 0 h (directly after application) and 1 h after application also as on day 1, 7 and 10 p.a.

Definition of risk- and burden-level

0	No or minimal risk/burden
1	Minor increase over minimal risk
2	Greater than minor increase over minimal risk

*Minimal risk/burden is defined as "*probability of harm or discomfort not greater than those ordinarily encountered in daily life or during the performance of routine physical or psychological examinations or tests".

Risk assessment

Issue	IMP	Routine physical or psychological examinations, daily life, standard treatment	Treatment in clinical trial with IMP	Risk level (treatment with IMP)
Adverse Events	Test product	Only very rare or rare. (Only transient AEs were reported in a previous study, also in general side effects after local use of mineral oils are rare.)	No other side effects than those already known are expected to occur. In contrast the treatment will be performed by trained study staff, thus over dosage and risks by misapplication will be limited. In case of allergic reactions immediate professional treatment will be provided, if necessary.	0
	Reference product GOLDGEIST [®] FORTE	Only very rare or rare. (Only transient AEs where reported in the leaflet of GOLDGEIST [®] FORTE predominantly involving the drug exposed parts of the skin.)	No other side effects than those already known are expected to occur. In contrast the treatment will be performed by trained study staff, thus over dosage and risks by misapplication will be limited. In case of allergic reactions immediate professional treatment will be provided, if necessary.	0
Affection of the lungs	Test product	Mineral oil aspirated into the lungs can cause pneumonia	Proper application of the IMP by trained staff will reduce direct contact with skin or aspiration into lungs.	0
	Reference product GOLDGEIST [®] FORTE	Pyrethrins can be absorbed through the lungs and skin.	Proper application of the IMP by trained staff will reduce direct contact with skin or aspiration into lungs.	0
Contact with eyes and mucous membranes (Violation against warnings and precautions)	Test product	Product is for external use only, contact with eyes and mucous membranes should be avoided.	Application by trained study staff will be done, preventing contact of the IMP with the eyes and mucous membranes. In case of accidentally contact the affected area will be carefully rinsed with a sufficient amount of clear water.	0

Issue	IMP	Routine physical or psychological examinations, daily life, standard treatment	Treatment in clinical trial with IMP	Risk level (treatment with IMP)
	Reference product GOLDGEIST [®] FORTE	Product is for external use only, contact with eyes and mucous membranes should be avoided.	Application by trained study staff will be done, preventing contact of the IMP with the eyes and mucous membranes. In case of accidentally contact the affected area will be carefully rinsed with a sufficient amount of clear water.	0

13.1.5.2 Burden assessment

Therapy with pyrethrum containing products as well as mineral oil containing products is an effective and recommended treatment of head lice infestation in patients of early infancy as well as for adults.

Handling and application of both investigational products in this study will be the same as given in the leaflets.

The design of the protocol takes into account the objective target of minimizing risks, distress and discomfort. The study site is staffed with experienced personnel knowledgeable in dealing with the medical and psychosocial needs of children. CardioSec provides a comfortable setting with age-appropriate furniture, food, and play equipment. Minor burden due to the study design are listed below and the level of burden is assigned.

Burden assessment

Issue	Routine physical or psychological examinations, daily life, standard treatment	Treatment in clinical trial with IMP	Burden level (treatment with IMP)
Time of visits	Usually first visit at a paediatrician or practitioner for diagnosing and initiating treatment, subsequent follow up visits to verify treatment success (necessary to regain permission to attend e.g. the kindergarten)	Visit times are minimized to a maximum of about 3 hours on study day 0 (for informed consent process, determination of head lice infestation as well as treatment) and shorter visits on study day 1, 7 and 10 (final examination); individual attendance at the clinical ward will be timed according to the needs of the paediatric patients and/or infant patient's guardian, time of waiting will be no longer than 30 minutes, play equipment suitable for children for their entertaining will be provided.	0
		Duration and extent of pre- and post- study examination does not differ significantly from common examinations necessarily done outside the clinical ward by a paediatrician or practitioner, when head lice infestation is diagnosed and treatment is indicated.	
Dry combing for assessment of hair scalp for living lice	Standard procedure with fine toothed lice comb procedure	Not different from investigation by a paediatrician or practitioner outside the clinical ward.	0
Hair washing procedure	Comparable with daily life	Not different to daily life (could be performed by the infant's guardian in case of very young patients, if necessary)	0
Application procedure and "time of taking effect"	Done according to the leaflet of the medical device recommended "time of taking effect": 10 minutes	Application will be done as recommended in the leaflet of the medical device "time of taking effect" will be 10 minutes.	0
	Done according to the leaflet of GOLDGEIST [®] FORTE recommended "time of taking effect": 30- 45 minutes	Application will be done as recommended in the leaflet of GOLDGEIST [®] FORTE "time of taking effect" will be 45 minutes.	0
Assessments of tolerability and safety	N.A.	Requires just a few minutes of elevated concentration and time	1

The level of burden will be carefully monitored by the study staff throughout the entire study, especially during the in-house periods. Properly trained and experienced personnel knowledgeable and skilled in dealing with the paediatric population and its age-appropriate

needs, including skills in performing paediatric procedures ensures an adequate and equal treatment of all patients and minimizes any potential risk, distress or discomfort.

13.1.6 Stop criteria in case of elevating risk/burden

The level of risk and burden will continuously monitored as it may evolve over time, during the trial and with evolving knowledge.

The test product **GOLDGEIST**[®] FORTE will be applied twice (day 0 and day 7) during the study. In case of AEs of non-tolerable degree, the treatment will be stopped. The investigational products will then be washed off and applicable treated if necessary.

14 Study population

Hundred (100) non-institutionalised patients of both genders \geq 1 year of age with a diagnosed head lice infestation will participate in the study.

The reference product **GOLDGEIST**[®] FORTE could be used without any age restriction. Therefore, infants under 1 year of age will not be enrolled in the study.

According to the following guidelines women should principally include in clinical research.

- Detailed guidance on the application format to be submitted to ethic committees (Guidance document to the EC directive 2001/20/EC; April 2004): justification for the selection of trial subjects.
- CIOMS/WHO International Ethical Guidelines, Guideline 16

Women as research subjects: "Investigators, sponsors, or ethical review committees should not exclude women of reproductive age from biomedical research. The potential for becoming pregnant during a study should not, in itself, be used as a reason for precluding or limiting participation...."

Both investigational products are intended for use in humans of both genders, therefore women should be included in the study, if this can be justified from a safety point.

The test product **GOLDGEIST**[®] FORTE there are no restrictions with respect to pregnant or breast-feeding women. Therefore, pregnant and lactating women will be not included into the study.

Special attention will be given to women with childbearing potential being enrolled in the study with respect to advice, examination and pregnancy testing. However women with childbearing potential will be requested to apply adequate contraceptive.

Patients will be enrolled in accordance with the following inclusion and exclusion criteria.

14.1 Inclusion criteria

To be eligible, the following inclusion criteria must be met:

- 1. Gender: male/female
- 2. Age: \geq 1 year of age at the time of signing the informed consent
- 3. Patients with active head lice infestation of at least 5 live lice and 5 apparently live eggs

- 4. Patient or his/her guardian must be capable of understanding and providing written informed consent
- 5. The patient or his/her legal representative must give written informed consent, after having been oral and written informed about benefits and potential risks of the trial, as well as details of the insurance taken out to cover the subjects participating in the study
- 6. Patients must agree to not use any other ant-lice treatment for the duration of the study
- 7. Female patients:

are women of childbearing potential who test negative for pregnancy and agree to use a reliable method of birth control or remain abstinent during the study. Methods of contraception considered acceptable include oral contraceptives, contraceptive patch, intrauterine device, vaginal ring, diaphragm with contraceptive gel, or condom with contraceptive gel

-or

are women of non-childbearing potential, defined as: women who have had surgical sterilization (hysterectomy, bilateral oophorectomy, or tubal ligation),

-or

women who are ≥60 years of age.

14.2 Exclusion criteria

A participant is not eligible, if any of the following exclusion criteria are present:

- 1. Known allergic reactions or hypersensitivity to the active ingredients used or the constituents
- 2. Patients with known skin allergies, multiple drug allergies or multiple allergies to cosmetic products
- 3. Pregnant or breast feeding women
- 4. Patient underwent treatment with any form of head lice treatment within the last 30 days prior to the Screening Visit (day 0)
- 5. Patients with chronic scalp disorder
- 6. Individuals on systemic or topical drugs or medications, including systemic antibiotics, which in the opinion of the investigative personnel may interfere with the study results
- 7. Subjects with hair longer than mid-back
- 8. Patients suspected or known not to follow instructions
- 9. Patients or his/her legal representative who are unable to understand the written and verbal instructions, in particular regarding the risks and inconveniences they will be exposed to as a result of their participation in the study
- 10. Previous participation in this study or participation in any other investigational trial within the preceding 30 days
- 11. The patients are investigator site personnel directly affiliated with this study and/or their immediate families. Immediate family is defined as a spouse, parent, child, or sibling, whether biological or legally adopted.
- 12. The patients are Oystershell employees or are employees of third-party organizations involved in the study.

The exclusion criteria are chosen to assure that patients with specific risks for administration of the investigated drug and patients with conditions that may have an impact on study parameters are excluded.

14.3 Method of assigning volunteers to treatment groups

This study will be randomised and investigator-blinded. When patients will arrive at the site they get a screening number. After the patient or his/her legal representative will give his/her written informed consent the patients will receive the subject number. Each patient who meets the inclusion and exclusion criteria will be assigned the lowest yet unassigned random number available at the centre. Randomisation will be performed during the Screening Visit V01 on day 0.

14.4 Blinding

As both products are substantially different from each other in terms of packaging, smell and application method, it is not possible to do a double-blinded trial. Both, the subjects and the clinic personnel that will apply the investigational products, will be able to recognize the products. Therefore, an investigator-blinded study will be performed, and an independent assessor (investigator or study staff performing the assessments of hair and scalp, eyes, as well the efficacy and safety evaluations) will be blinded to the treatment [20]. Appropriate measures will be taken to keep the assessor blind during the whole study. The assessor will not be involved in any procedure of the trial involving the handling, storage, and use of the products.

14.5 Removal of volunteers from treatment or assessment

Withdrawal criteria

- Serious Adverse Events (SAE's)
- Diseases requiring treatment that occur during the study, which do not constitute SAE's but which, in the opinion of the Principal Investigator, would probably prevent achievement of the study objectives.
- Non-adherence to the study conditions or relevant deviations from procedures as established in the study protocol.
- Withdrawal of consent.
- Duration of treatment < 10 minutes for **GOLDGEIST[®]** FORTE.
- Severe irritation of the skin or the eyes on pre-treatment assessment on day 7
- Use of any other anti-head lice therapy.

All details and reasons for removal of trial subjects from the study will be recorded in the study termination section of the CRF. CRFs of all trial subjects entered into the study have to be kept in the documentation of the study. Reasons for withdrawal of trial subjects will be entered into the final report of the study. Every effort has to be made to follow-up trial subjects who terminate with drug-related AE's in order to determine the final outcome.

Follow-up of withdrawn patients, drop outs

A drop out is a patient, who prematurely discontinues participation after being enrolled. If a patient drops out, possible PTSS (Pre-treatment Sign and Symptom) or AE's will be recorded as long as necessary. A post-study examination should be performed if possible.

All PTSS/AE's documented during the study for the drop out will be considered in the assessment. Other data recorded for the drop out are contained in the individual patient listing in an appendix to the study report.

Replacements

Patients who prematurely discontinue participation will be replaced.

Removal of volunteers from assessment

Screening failures

Screening failures are volunteers who were screened but not enrolled.

Screening failures including reason will be listed in the screening list. All data obtained within the screening will be documented in the patient's record. In case that entries were made to a CRF it will be archived, but not entered in the database.

Screening failures will not be listed, as no CRF data is included in the database.

Safety set

The safety set/population consists of all patients who were randomised and exposed to study medication.

Per-protocol set

All subjects

- without any major protocol violation
- with available values of the relevant study variables

will be included in the per-protocol-set/population.

Comprehensive justification for the classification of a protocol violation as "major" will be given in the integrated clinical study report.

Premature Termination of the study

The sponsor has the right to close this study, and the Principal Investigator has the right to close the centre, at any time, although this can occur only after consultation between involved parties. The IEC/IRB would be informed. If the study/centre had to be closed prematurely, CardioSec GmbH would provide all essential documents necessary for the sponsor's TMF as defined in the GCP Note for Guidance.

The trial will be terminated prematurely in the following cases:

- If AE's occur which are so serious that the risk-benefit ratio is not acceptable.
- If the trial conduct (e.g. recruitment rate, drop-out rate, data quality, protocol compliance) does not suggest a proper completion of the trial within a reasonable time frame.

15 Clinical performance of the study

15.1 Definition of study periods

The study will consist of 4 visits:

Screening visit (V01) lasts from the time point of the patients' arrival at the study centre until assessments 1 hour after end of administration of the investigational products.

The study day 0 comprises patient information, obtaining of age-appropriate assent or written informed consent, checking of in- and exclusion criteria, documentation of demographic data,

documentation of medical history, documentation of pre-existing or concomitant diseases or medication, physical examination of the scalp to verify head lice infestation, decision regarding study inclusion, pregnancy urine test, baseline-assessment of skin and eyes irritation, randomisation, administration of IMP by study staff and assessments for tolerability and questioning on satisfaction with the \geq 1 hour after end of administration.

Evaluation visit (V02) starts 24 hours (day 1) after end of application. On study visit 2 assessments for tolerability and efficacy will be performed.

Second Treatment visit (V03) starts 7 days (day 7) after end of first application. Assessments for tolerability and efficacy and a second administration of the investigational product will be performed. The second treatment will be performed only in patients without severe irritation of the skin or the eyes in the pre-treatment assessment.

The study ends for the individual patient after he/she underwent the **Follow-up visit (V04)** on day 10, unless any Adverse Event requires further observation.

Patients will be instructed to contact the investigator as soon as possible if they have a complaint or problem with the investigational product so that the situation can be assessed.

All procedures to be conducted during the study, including timing and sequence (as necessary) of all procedures, are indicated in the Flow chart (see chapter 3).

15.2 Study Visits and measures

15.2.1 Screening Visit V01 (day 0): study initiation, registration, enrolment, randomisation, first administration

Patients with suspicion of head lice infestation will be recruited for this study. Written informed consent will be obtained from adult patients or the legal representative of minors. Children able to read and write have to give their assent in written. The assent of younger children will be given verbally as far as appropriate.

Patient's eligibility for participation in the trial will be established by the investigator prior to enrolment.

Demographic data (gender, subject age, hair length (short, shoulder long, mid-back, long), medical history, PTSS during the last week prior to the intended administration of the investigational products, concomitant diseases and concomitant medication (especially chronic medications and use of medications including OTCs during the last 1 weeks, and use of anti-head lice treatments) will be recorded.

Body weight and height will be determined.

The diagnosis head lice infestation will be confirmed by:

• identification of at least five living lice or nymph (immature forms) and five live eggs

The study staff will examine the entire scalp and head hair as described in 15.5.6. Every part of the hair will be examined and the findings will be documented in the CRF:

The severity of head lice infestation will be judged on a 4-point severity scale:

- 0 = no relevant infestation (0-4 lice and/or nymph present);
- 1 = mild (5-9 lice and/or nymphs present);
- 2 = moderate (10-24 lice and/or nymphs present);

• $3 = \text{severe} (\geq 25 \text{ lice and/or nymphs present}).$

Patients will be considered eligible for participation in the study if they do meet any of the inclusion and none of the exclusion criteria. Patients will be received a subject number in ascending order.

In order to ensure administration and precise efficacy and tolerability assessments the patients will be housed at the study site until the assessments 60 minutes after the end of administration have been finished.

The investigational products will be applied at the centre by un-blinded either physicians or specially-instructed nursing staff (see 15.4.

Date and times of start and end of application of the investigational product and times of tolerability and efficacy assessments will be documented.

To sum up, at visit 1 the following operations will be performed and/or parameters controlled by the study team:

- Age-appropriate patient information and obtaining of written informed consent or oral assent
- Documentation of demographic data
- Documentation of medical history
- Documentation of pre-existing or concomitant diseases, PTSS
- Documentation of pre-existing or concomitant medication
- Verifying of head lice infestation, incl. severity
- Checking of inclusion and exclusion criteria including pregnancy test if applicable
- Decision regarding study inclusion, randomisation
- Baseline assessments
- First application of the investigational product
- Post-treatment assessments directly after start of treatment, as well as 1 hour after removing the investigational product
- Questionnaire on the satisfaction with esthetical effect of the products

After the assessments the patient is released from the clinical ward and advised to follow the restrictions made in the protocol and to come back on the next day for the second visit.

15.2.2 Evaluation Visit V02 (day 1): 24h p.a.

24 hours (\pm 3h) after end of study drug administration the patients will attend the study site. After the 24-hour interval the patient or his/her guardian will perform the efficacy and tolerability assessments.

These data, any concomitant medication taken during the study period, adverse events and any change in concomitant diseases will be recorded in the CRF.

Therefore, at visit 2 the following operations will be performed:

- Hair scalp assessment for living lice (all stages) by study staff
- · Assessments of skin and eyes irritation, local tolerability
- Questioning on general well-being
- Questioning on patient's combing

• Registration and documentation of any adverse event and/or changes regarding concomitant diseases, concomitant medication, withdrawal criteria

In case that the examination of the hair and scalp (diagnostic combing) will show active head lice infestation, the life stage of the lice will be documented. The patients will be instructed to use a lice comb until second treatment on day 7.

15.2.3 Second Treatment Visit V03 (day 7)

On study day 7 (V03; +1 day) the scalp and hair will be examined for live head lice by blinded study staff. The life stage of the lice will be documented. The assessments of skin and eyes irritation within 1h prior to administration will be performed. Patients without severe skin or eyes irritations will receive a second treatment with the assigned test product.

The patients will be asked for any concomitant medication taken during the study period and adverse events that occurred.

At visit 3 the following operations are being performed by the study team:

- Hair scalp assessment for living lice (all stages) by study staff
- · Second application of the investigational products by the study staff
- Assessments of skin and eyes irritation, local tolerability
- Questioning on well-being
- Questioning on patient's combing
- Registration and documentation of any adverse events and/or changes regarding concomitant diseases, concomitant medication, withdrawal criteria
- Questionnaire on the satisfaction with the esthetical effect of the products

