	11. To evaluate eye irritation by study staff on day 0, 1, 7 and 10
	 To evaluate characterisation of safety and tolerability of the investigational products considering Adverse Events in the study population
Efficacy variables	Cure rate at the end of day 10 (corrected for re-infestation) for the test product for all baseline infestations (primary parameter)

	 Cure rate at the end of day 10 (corrected for re-infestation) for the reference product GOLDGEIST[®] FORTE for all baseline infestations (secondary parameter)
	Difference of cure rates (secondary parameter)
	 Cure rate at day 10 (corrected for re-infestation) for mild and moderate baseline infestations, (secondary parameter)
	 Cure rate at day 1 for the test product for all baseline infestations (secondary parameter)
	 Cure rate at day 1 for mild and moderate baseline infestations, (secondary parameter)
Safety variables	 Local tolerability: subjective symptoms (burning, paraesthesia, pruritus): 0d (0h, 1h), 1d, 7d (0h, 1h) and 10d p.a. by patient (secondary parameter)
	 Global tolerability assessment at 10d by patient and study staff (secondary parameter)
	 Skin irritation assessment: 0d (0h, 1h), 1d, 7d (pre-treatment, 0h, 1h) and 10d p.a. (secondary infection, erythema, excoriation) by study staff (secondary parameter)
	 Eyes irritation assessment: 0d (0h, 1h),1d, 7d (pre-treatment, 0h, 1h) and 10d p.a. by study staff (secondary parameter)
	 Questioning on general well-being and Adverse Events (AEs): 0d (0h, 1h), 1d, 7d (0h, 1h) and 10d p.a. (secondary parameter)
Patient recorded outcomes	 Questioning on the satisfaction with the esthetical effect of the anti- lice products by patient: day 0 and day 7 after treatment and hair drying (secondary parameter)
Pharmacokinetic variables	Not applicable
Statistical methods	Descriptive statistics of all endpoint variables will be tabulated (continuously scaled variables: mean, standard deviation, median, min, max, categorically scaled variables: counts and percentages) by visit and treatment.
	Populations
	Safety population (SAF): All enrolled subjects who administered the investigational product, independently of the duration of treatment.
	Per-protocol population (PP): All enrolled subjects, who show no major protocol deviations (to be defined before database lock). All subjects who provide valuable data.
	Hypotheses
	The primary aim of the study is to show superiority for the cure rate of investigated treatment p_T versus a predefined limit of 70%.

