Global tolerability assessment by blinded study staff and patient						•
Local tolerability assessment (subjective symptoms: burning, paraesthesia, pruritus) by the patient ^D		•	•	•	•	•
Skin irritation assessment: secondary infection, erythema, excoriation by blinded study staff ^D		•	•	•	•	•
Hair scalp assessment for living lice (all stages) by blinded study staff				•	•	•
Eyes irritation assessment by blinded study staff ^D		•	•	•	•	•
Questioning on general well- being by blinded study staff		•	•	•	•	•

Procedure Screening Visit V01					Second Treatment Visit V03	Follow-up Visit V04	
Study day	Day 0			Day 1 (±3h)	Day 7 (+1d)	Day 10 (-1d; +2d	
	-2h	0h	+1h	24h after end of administration (±3h)			
Questioning on AE by blinded study staff	•		•	•	•		
Questioning on patient's combing		•	•	•			
Check of restrictions				•	•	•	
Questioning on satisfaction with the esthetical effect ^E	•			•			
Discharge from clinical study						•	

^A Pregnancy tests (urine) will be performed in all female patients with childbearing potential prior to study start

^B Baseline assessments within 1h prior to administration on day 0 and day 7, on day 7 the pre-treatment assessment for irritations (skin, eyes) have to be used for decision about withdrawal due to severe irritation

^C The time of exposure to the investigational products on the uncovered hair will not exceed 10 + 2 minutes for the test product and 30 – 45 + 5 minutes for the reference product GOLDGEIST[®] FORTE

^D Assessments after administration will be performed directly after start of the treatment plus 5 minutes as well as after the end of administration (the contact time is over and the investigational product is rinsed) within 15 minutes.

^E Satisfaction with the esthetical effect will be performed on day 0 and day 7 after treatment and hair drying by the patients

For all other assessments a deviation up to ± 20 min from scheduled time will be accepted.

4 Signature pages

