15.7.2 Checks for general well-being

The observation phase for PTSS will start one week prior to the first intended study drug administration, for AE's with signing the informed consent, and will end with the release of the subject from the study examination.

Checks for general well-being will be performed in a non-leading manner. In addition to the checks for general well-being at the first visit (0h, 1h p.a.), checks will also be performed, on study day 1 as well as on study day 7 (0h, 1h p.a.) and at the final visit on study day 10.

A registered physician will be available throughout the entire study and all patients will be observed for signs of clinical toxicity during the entire study.

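### No rule requires the second application to be withheld after a tolerated or resolved rash or allergic reaction to the first, and AE questioning is not fixed before dosing on day 7

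*Protocol*

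**What the plan says.** Four places in the protocol set the irritation condition for dose two, and they agree.

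- Section 15.2.3: "Patients without severe skin or eyes irritations will receive a second treatment with the assigned test product".
- Flow chart, footnote B: "on day 7 the pre-treatment assessment for irritations (skin, eyes) have to be used for decision about withdrawal due to severe irritation".
- Section 14.5, withdrawal criteria: "Severe irritation of the skin or the eyes on pre-treatment assessment on day 7".
- Section 15.1 allows the second treatment only where the pre-treatment check shows no severe irritation.

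On the timing of safety questions, the synopsis (safety variables) lists "Questioning on general well-being and Adverse Events (AEs): 0d (0h, 1h), 1d, 7d (0h, 1h) and 10d p.a". The skin score has an extra slot there: "Skin irritation assessment: 0d (0h, 1h), 1d, 7d (pre-treatment, 0h, 1h) and 10d p.a". The eye score has the same extra slot. Section 13.1.5.1 explains the time label: "checks for general well-being will be performed at 0 h (directly after application) and 1 h after application". Section 15.7.2 gives the well-being checks the same times, "on study day 7 (0h, 1h p.a.) and at the final visit on study day 10". The visit text in 15.2.3 says "The patients will be asked for any concomitant medication taken during the study period and adverse events that occurred", with no time attached.

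Section 13.1.2.1 reproduces a leaflet warning for the test product: treatment is to stop at once if a rash or signs of irritation or allergy appear. It gives no severity threshold. Sections 11, 13.1.4 and 13.1.5.2 say the products are used as their leaflets or instructions direct.

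**The concern.** The design re-exposes every patient a week after the first application, in a population that starts at age 1. Section 14.2, criterion 1, keeps out anyone with a known allergic reaction to the ingredients before dose one. After dose one the trial itself may have produced such a reaction, yet no equivalent bar is required before dose two. Both products carry an allergy-related warning (13.1.2.1 and 13.1.2.2), and 15.8.1 plans treatment for allergic reactions, so the event is foreseen.

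Two things are missing: a rule that acts on a reaction to dose one that is not severe on day 7, and an assurance that the history of days 2 to 7 is known before the product goes on. What is at stake is the safety of a very small number of patients. The efficacy analysis is not affected.

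**Working it through.** **Which patients the rule lets through.** The skin and eye scales (15.5.3, 15.5.4) run from 1 (no) to 4 (severe). Only score 4 at the day 7 pre-treatment check bars dose two, so these patients pass:

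- a patient scored 2 or 3 on day 7;
- a patient whose rash or allergic reaction after day 0 has resolved by day 7.

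**Whether another provision requires withholding for them.**

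- Serious AE (14.5): mandatory, but for serious events only.
- Disease requiring treatment (14.5): rests on the Principal Investigator's opinion, and concerns whether the study objectives can be met, not the risk of re-exposure.
- AE of non-tolerable degree (13.1.6): does not cover tolerated reactions.
- Concomitant medication review (15.8): reached only if the reaction was medicated, and discretionary.
- Action-taken entry (15.7.3.2): a record, not a rule.
- Patient contact with the investigator (15.1), physician availability (15.7.2) and paediatric supervision (22.3): oversight without a decision rule.

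None requires withholding after a non-serious reaction that was tolerated or has resolved.

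**What is known before dose two.** Skin and eye scores have a day 7 pre-treatment slot. AE questioning has only 0h and 1h in the synopsis, and 15.2.3 leaves the order open. AE information is therefore certain to be on file before dose two only from the day 0 and day 1 visits.

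**Size.** The protocol states no figure for this, so only a bound is possible. Inputs:

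- n = 50 per arm (16.5).
- Reference product (13.1.2.2): local skin irritation is classed as rare, at most 1/1000; contact sensitivity as very rare, at most 1/10000.
- Test product (13.1.5.1): AEs are called rare or very rare, with no scale. Assumption: the reference leaflet's scale applies, so at most 1/1000.

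Expected number = n × p. Chance of at least one = 1 − (1 − p)^n.

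- n = 50, p = 1/1000: 0.05 patients; 1 − 0.999^50 = 4.9%.
- n = 50, p = 1/10000: 0.005 patients; 1 − 0.9999^50 = 0.5%.
- n = 100, p = 1/1000 in both arms: 0.1 patients; 1 − 0.999^100 = 9.5%.

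These are upper bounds. They count reactors before any other provision removes them.

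**Effect of withholding.**

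- One patient in 50 is 1/50 = 2.0 percentage points of an arm's cure rate, if treatment then fails. At 0.05 patients the expected loss is at most 0.05 × 2.0 = 0.1 point per arm.
- A held-back patient with live lice waits for other therapy until the day 10 visit, because 15.3 bars parallel treatment: nominally 10 − 7 = 3 days. With the visit windows (day 7 +1; day 10 −1/+2) the shortest wait is 9 − 8 = 1 day and the longest 12 − 7 = 5 days.

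**The case against.** The strongest reply is that clinical judgement already covers this. A registered physician is available throughout, an experienced paediatrician supervises everything concerning minors, and risk is monitored continuously. Day 1 collects AEs and skin, eye and tolerability scores, and skin and eyes are scored again before dosing on day 7. Much of this stands: a sensible investigator would probably hold back in an obvious case. But it leaves the outcome to discretion, while the written rule points towards giving dose two.

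Three stronger readings are tempting, and the documents do not support them.

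- *That dose two must be given to everyone without severe irritation.* The wording of 15.2.3 might suggest it, but 15.1 makes the absence of severe irritation a necessary condition, and an investigator may still withhold.
- *That AEs are asked about only after the day 7 application.* This rests on the synopsis list and on an explanation of 0 h given for well-being checks. The flow chart's day 7 column is undivided, and its day 0 0h column also holds randomisation and baseline scores. The items in 15.2.3 are not in time order. One item there joins AEs with withdrawal criteria, part of which must be checked before dosing. What stands is that the order is not assured.
- *That the protocol breaches the leaflet.* The stop instruction stands beside rinsing and contact-time advice and may mean only the application in progress; 13.1.6 similarly speaks of washing the product off. It is quoted for the test product only. Even so, nothing then addresses re-exposure a week later.

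It is also fair to say that the number affected is tiny and that its bound is partly assumed.

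**Conclusion.** The point holds as a minor safety improvement that the sponsor could make. A patient with a non-serious rash or allergic reaction to dose one can be re-exposed without departing from any written rule, and the information needed to decide otherwise is not guaranteed to be in hand. This rests on reading the four concordant statements of the rule together with the other stop provisions. The size rests on the leaflet frequency bounds, borrowed for the test product. It is a reason to tighten the day 7 procedure, not a reason to doubt the trial's conclusions.

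**What to change.** 1. In 15.2.3, the synopsis and the flow chart, place AE questioning and the check of withdrawal criteria before the day 7 application, and read the answers with the day 0 and day 1 scores.

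2. In 15.1, 15.2.3, footnote B and a note after the withdrawal list in 14.5, keep the severe criterion and add for both arms: the second application is also withheld if a rash or allergic reaction assessed as at least possibly related to the product (scale in 15.7.3.2) has occurred since day 0. Transient burning or redness alone, and irritation present at baseline or due to the infestation, do not count.

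3. State that patients held back under this addition attend day 10, are not replaced (14.5 otherwise replaces patients who discontinue), and stay in the 16.3 denominator and the ITT analysis. Fix their per-protocol status before database lock, because section 17 uses that set for non-inferiority.

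The rule is the same in both arms, so it does not tell the blinded assessor which product was used. The exemption keeps the mild transient effects already reported for the test product from triggering it. Mild or moderate irritation on day 7 that is neither a rash nor an allergic reaction would still allow dose two, as now.

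The cost is one sentence in four places, the note on follow-up and analysis, one question moved ahead of dosing, and one line on the day 7 CRF page. The downside is that a held-back patient receives one application and, if live lice remain, bears the wait shown in the working.
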